## **Specification of outcomes**

### *Primary endpoint:*

The primary endpoint is postoperative increase of NT-proBNP from the day before surgery to the third postoperative day.

.

### *Secondary endpoints and substudies*

Secondary endpoints are the absolute levels of NT-proBNP on postoperative day 1 and day 3.

### **Subgroup analyses and substudies**

Patients undergoing isolated CABG or CABG with concomitant procedure will also be analyzed separately.

Blood samples from the three sampling time points are planned to be frozen to permit analysis of novel markers of heart failure and myocardial injury in the future.

Minor substudies may arise but will be specified and reported to the Swedish MPA and ClinicalTrials.gov before they are started.

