## Study population

- Patients accepted for CABG of at least two vessel disease or left main stenosis with or without a concomitant procedure and who either have:
  - EuroSCORE II  $\geq$  3.0 to which at least one of following risk factors contribute
    - LVEF  $\leq$  0.50
    - CCS-class IV
    - Myocardial infarct  $\leq$  90 days
    - Emergent or urgent procedure
    - CABG + aortic or mitral valve procedure
  - Left Ventricular Ejection Fraction  $\leq$  0.30 regardless of EuroSCORE II
- The procedure has to be done with heart-lung machine (on-pump)

These patients will be informed about the trial and asked to participate. Patients who accept participation and are operated with the aid of heart-lung machine will be included in the study.

Exclusion criteria: patients with ambiguous food allergy known to have triggered shortness of breath, rash or flushing, age >85 years, previous cardiac surgery, informed consent not possible because of critical condition, linguistic or other reason, renal failure with preoperative dialysis or calculated GFR < 30 mL/min, preoperative use of mechanical circulatory assist, surgery without heart-lung machine (off-pump), concomitant Maze-procedure for atrial fibrillation, surgery of ascending aorta, surgery of both aortic and mitral valve.

The participating centers Linköping, Örebro, Umeå, Gothenburg, Uppsala and Karlskrona are the only cardiac surgical centers within their region and thus account for all cardiac surgical procedures. To evaluate sampling bias the aim is to use the databases from each center.

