## **Research plan**

Randomized double-blind study on 310 patients fulfilling inclusion criteria. Randomization will be stratified for those undergoing isolated CABG and those undergoing CABG with concomitant procedure.

Half of the patients will receive glutamate infusion intravenously (1.65 mL/ kg bodyweight and hour of a 0.125M L-glutamic acid solution), which will be started 10-20 minutes before anticipated release of aortic cross-clamp and the start of reperfusion. The infusion will be given for 2 hours after release of aortic cross-clamp. Thereafter another 50 mL will be given with the infusion rate halved. The maximum total given will not exceed 500 mL. If the volume is insufficient due to high body weight or extension of cross-clamp time the last 50 mL should be given at half the original infusion rate. The remaining half of the patients will receive normal saline in a similar way.

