### **Sample size estimation and statistics**

The sample size is based on available results on NT-proBNP from the first GLUTAMICS-trial. In that study the following increase of NT-proBNP was observed in patients undergoing CABG or CABG with concomitant procedure who fulfilled inclusion criteria for the planned trial from preoperative values to postoperative day 3 (mean  $\pm$  Standard Deviation)

Glutamate (n=71):  $5261 \pm 4409$

Placebo (n=62):  $7112 \pm 6454$

Sample size estimation by statistical expertise (80% power, 5% risk level; two-sided test) suggests 141 patients in each group. To compensate for possible missed sampling and other causes for loss of data we plan to include a total of 310 patients.

Interim analysis will be performed by an independent external statistician after 160 patients in a way that does not increase the demands regarding statistical significance of the primary endpoints. An adaptive design implying that a surrogate variable (increase of NT-proBNP from preoperative level to postoperative day 1) known to correlate well with the primary endpoint will be used. Furthermore, regardless of if statistical significance is reached the study will proceed until 310 patients have been included or until the expiry date of the study solutions. Stopping criteria are given on page 12.

Continuous variables will be analyzed with a two-tailed t-test or Mann-Whitney U test depending on the distribution of data.

**STUDY PROTOCOL:** English translation - Study protocol version 5 2016-08-01 to the Swedish Medical Product Agency

Categorical variables will be analyzed with a two-tailed Chi square test unless expected cell counts are less than 5, then Fisher's exact test will be used.

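### The two randomisation strata are to be analysed separately, with no treatment-by-stratum interaction and no rule for reading discordant results, so the plan cannot show whether the effect differs between them

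*Combined protocol and SAP*

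**What the plan says.** Under Research plan the protocol states: "Randomization will be stratified for those undergoing isolated CABG and those undergoing CABG with concomitant procedure". Under Subgroup analyses and substudies it adds: "Patients undergoing isolated CABG or CABG with concomitant procedure will also be analyzed separately". That sentence names no endpoint, test, estimate or interpretation rule.

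The general rule under Sample size estimation and statistics is: "Continuous variables will be analyzed with a two-tailed t-test or Mann-Whitney U test depending on the distribution of data". Both tests compare two groups and carry no stratum term. The same section sizes the trial for the overall comparison only: "Sample size estimation by statistical expertise (80% power, 5% risk level; two-sided test) suggests 141 patients in each group". The enrolment target adds an allowance for lost data: "To compensate for possible missed sampling and other causes for loss of data we plan to include a total of 310 patients".

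The documents contain no interaction test, stratum-adjusted model, expected share of isolated CABG or stratum-level power.

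**The concern.** Two separate tests answer two questions of the form: is there an effect in this stratum? Neither asks whether the effect differs between strata. With about half of the patients or fewer in a stratum, chance and stratum size alone can put one result below 5% and the other above it. Such a pair is easily reported as benefit in one kind of surgery and none in the other.

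The Background section shows how readily this happens. It names diabetics as the exception to the large risk reductions seen in high-risk groups of the first trial, and Table 1 supports this with separate subgroup p-values (0.89 in diabetics, 0.02 in non-diabetics). An approximate interaction test on the same counts does not reach 5% (see the end of the working). The Background also says that the first trial's findings drew little attention because they were secondary endpoints in subgroups. A confirmatory trial should not leave its one named subgroup comparison open to the same weakness.

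**Working it through.** **Inputs** (Sample size estimation and statistics, unless noted)

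- Increase in NT-proBNP to day 3 in the first trial: glutamate 5261 ± 4409 (n=71), placebo 7112 ± 6454 (n=62).
- Two-sided 5%, 80% power, 141 per group. 1:1 allocation (Research plan: "Half of the patients will receive glutamate infusion intravenously").
- Share f of isolated CABG: not given. Assumed 50% to 80%.
- Also assumed: the same absolute effect and SD in both strata, and a t-test in each.

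**1. Reproduce the plan's figure.** Difference = 7112 − 5261 = 1851. SD = √[(4409² + 6454²)/2] = 5527. Standardised difference = 1851/5527 = 0.335. The normal formula 2 × [(1.960 + 0.842) × 5527/1851]² gives 140 per group. The noncentral t gives 80.0% power at 141, so the plan's 141 is reproduced.

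**2. Power in each stratum.** With n = 141f or 141(1 − f) per arm, the noncentrality is 1851/[5527 × √(2/n)]. Call the two powers p₁ and p₂. The strata are independent, so exactly one significant = p₁(1 − p₂) + p₂(1 − p₁), both = p₁p₂, neither = (1 − p₁)(1 − p₂).

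| Isolated : concomitant | p₁ | p₂ | Exactly one | Both | Neither |
|---|---|---|---|---|---|
| 50:50 | 50.6% | 50.6% | 50.0% | 25.6% | 24.4% |
| 60:40 | 58.2% | 42.2% | 51.3% | 24.5% | 24.2% |
| 70:30 | 64.8% | 33.1% | 55.0% | 21.5% | 23.5% |
| 80:20 | 70.7% | 23.5% | 61.0% | 16.6% | 22.4% |

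If all 310 patients are evaluable, exactly one is significant in 50% (50:50) to 62% (80:20). If the SD with a concomitant procedure is 1.25 to 2 times that in isolated CABG, with the overall SD kept at 5527, the range is 52-79%.

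**3. Other true effects, still equal in both strata (282 evaluable).**

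| True effect ÷ 1851 | Most frequent outcome for splits 50:50 to 80:20 |
|---|---|
| 0.5 | Neither, about 69% at every split (exactly one: 28-29%) |
| 0.75 | Neither up to 70:30 (47% against 43% at 50:50); exactly one at 80:20 |
| 1.0 | Exactly one at every split |
| 1.25 | Both at 50:50 and 60:40 (48% against 42% at 50:50); exactly one from 70:30 |
| 1.5 | Both up to 70:30 (71% at 50:50, 59% at 70:30); exactly one at 80:20 |

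**4. What an interaction analysis could show.** SE of the between-stratum difference in effect = 5527 × √[2/(141f) + 2/(141(1 − f))]. This is 1316 at 50:50 and 1646 at 80:20, or 71% and 89% of 1851. If the true effects differ by the full 1851, power is about Φ(1851/SE − 1.96): Φ(1.41 − 1.96) = 29% at 50:50, and Φ(1.12 − 1.96) = 20% at 80:20. If the effects are equal on the scale of analysis, the test signals a difference in 5% of trials.

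**5. The diabetes example (Table 1).** Diabetics: 4/98 against 4/108, log RR 0.097, variance 1/4 − 1/98 + 1/4 − 1/108 = 0.481. Non-diabetics: 2/313 against 12/305, log RR −1.818, variance 1/2 − 1/313 + 1/12 − 1/305 = 0.577. z = (0.097 + 1.818)/√(0.481 + 0.577) = 1.86, p ≈ 0.06. This is approximate, because events are few.

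**The case against.** The strongest case against has five parts.

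- **The headline probability depends on the effect.** A reader might infer that a discordant pair is the likeliest result whenever glutamate works equally in both strata. Step 3 does not support that. The planned effect is itself uncertain: 1851 ± 1.96 × √(4409²/71 + 6454²/62) gives about −55 to 3757. This stands, and the figures must be tied to the planned effect.
- **The plan does not say it will compare p-values.** A reader might infer that the sponsor intends to claim a differential effect from discordant tests. The subgroup sentence says only that the groups are analysed separately. This stands too: the defect is a missing analysis and a missing rule, not a stated wrong inference.
- **The analysis is limited in scope.** It is one prespecified factor and the randomisation stratum itself, and a supplementary subgroup need not be powered alone. This stands. Low stratum power is not a fault in itself. It matters because nothing guards the interpretation.
- **An interaction model is not a drop-in replacement.** Mann-Whitney has no interaction term, and the SDs are close to the means (4409 against 5261, 6454 against 7112), so skewness is likely. Interaction also depends on scale: if increases are larger after combined surgery, an equal proportional effect appears as unequal absolute effects. This stands, and the scale must be prespecified.
- **Putting the stratum in the main analysis is a separate matter.** The probabilities above do not argue for it. The reason is that the analysis should reflect the stratified randomisation, and one model can serve both purposes.

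**Conclusion.** The concern holds in a limited form. The plan analyses its two randomisation strata separately, with no interaction analysis and no rule for discordant results, so it cannot show whether the effect differs between them. That part rests on the text alone.

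The size rests on assumptions: a true effect of 1851 equal in both strata, a common SD of 5527, t-tests, 282 evaluable patients and 50-80% isolated CABG. Under these, exactly one stratum is significant in about 50-61% of trials and both in about 17-26%. At half the planned effect, neither leads at about 69%. At 1.5 times it, both leads for splits up to 70:30. Mann-Whitney on skewed data would change the figures.

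A reader might also infer that the primary result is compromised. It is not: the unadjusted overall comparison remains valid, and the point concerns how the subgroup results are analysed and read.

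**What to change.** Before unblinding, replace the separate-analysis sentence with a short paragraph:

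1. Analyse NT-proBNP in one linear model with treatment, stratum and treatment-by-stratum interaction, on a scale fixed in advance. If the data are expected to be skewed, one option is the log day-3 value adjusted for log baseline.
2. Report the treatment effect in each stratum with its 95% CI, and the interaction estimate with its CI.
3. State that significance in only one stratum will not be read as a differential effect, and that a non-significant interaction will not be read as proof of equal effects.
4. Include the randomisation stratum as a factor in the main analysis, without the interaction.

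The cost is a few sentences and little analysis work, with no extra patients or data. The choice of scale needs thought: a log model estimates a ratio rather than a difference in absolute increase, so its relation to the primary endpoint must be stated. The main limit is power, about 20-29% for a between-stratum difference of 1851, so the intervals should lead the report.

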### *Safety variables*

Postoperative mortality (30 days + in-hospital), stroke within 24 hours of surgery and SUSAR.

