## **Overall assessment of risk and benefit**

Glutamate has metabolic properties that can increase myocardial tolerance to ischemia and enhance recovery of metabolism and function after ischemia(2, 6). These properties are desirable when conventional pharmacologic al treatment and myocardial protection is insufficient. The need for alternative treatment is strengthened by the fact that traditional treatment of postoperative heart failure with inotropic drugs increase myocardial oxygen consumption excessively in relation to the effect on myocardial contractility and hence carries a risk of aggravating underlying ischemic myocardial injury(2, 25, 26). This could explain why postoperative heart failure has been identified as the single most important cause for postoperative mortality after CABG(1). In the first GLUTAMICS trial a relative risk reduction exceeding 50% of developing heart failure leading to extended intensive care or death was observed in most high-risk groups (table 1)(13).

Potential hazards include the adverse reactions reported on pages 11-12. The risk of adverse reactions, such as Chinese restaurant syndrome, asthma or urticaria is considered small with the dosages employed and will be further reduced by excluding patients with ambiguous food allergies. In our twenty-year experience with glutamate including the first GLUTAMICS trial we have so far not observed any of these adverse reactions. In light of this we consider the potential benefits to outweigh the potential hazards.

The investigators manual provides more details and references.

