In a neurotrauma cohort conventional amino acid solutions containing glutamate 3.75 gram/L was found to increase plasma levels of glutamate twice but no difference in outcome was found between patients receiving amino acids vs those not receiving amino acids(34).

In this context it might be worth considering that glutamate concentrations in the central nervous system are approximately 50 times higher than in blood(21). The glutamate infusion planned in our trial increases blood levels 2-3-fold(22).

In the first GLUTAMICS-trial involving 861 patients the risk for subclinical neurological injury was evaluated in a subgroup by sampling of biomarker S-100B. No differences or trends were found between the glutamate and control group regarding S-100B or clinical neurological events(35).

Despite being a natural amino acid in the human body adverse reactions and allergy has been discussed. It is mainly three conditions that has caught the eye in the medical literature. These are Chinese restaurant syndrome, glutamate elicited asthma and glutamate elicited urticaria. Chinese restaurant syndrome has received most attention (flushing, headache and chest pain). Several blinded studies, some of them done on patients who have claimed to have experienced

**STUDY PROTOCOL:** English translation - Study protocol version 5 2016-08-01 to the Swedish Medical Product Agency

symptoms related to glutamate, have failed to prove the connection as no difference in symptoms were found between patients receiving glutamate or not(36-38). Similar findings have been done in patients claimed to have glutamate elicited asthma(39, 40). There are studies suggesting that glutamate could cause Chinese restaurant syndrome in susceptible individuals(17). Although, there is reason to question the latter studies we have decided that ambiguous food allergies known to have elicited flushing, headache, rash or asthma will be exclusion criteria in the planned trial.

More details and references are given in the supplement about adverse reactions and toxicology.

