### **Adverse events (AE)**

Adverse events (AE) are common after cardiac surgery as all patients have some degree of postoperative pain, bleeding and fever. Serious adverse events (SAE) are defined as AE that have been life threatening or deadly or resulted in extended hospital care or permanent sequelle. SAE are also common after cardiac surgery. Postoperative atrial fibrillation, the most common cause for exended hospital stay, is observed in approximately one third of the patients undergoing CABG.

In GLUTAMICS II AE will be registered and dived into AE and SAE. To determine if the study substance had any influence on AE these events will be compared between treatment group and control group. AE will be reported according to what organ has been affected: Central nervous system, heart - circulation, lungs, gastrointestinal tract, kidneys, skin. Infections will be reported according to would or organ affected. Postoperative nausea will be reported if it required antiemetic treatment.

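### The infusion reactions that the protocol names as hazards are neither a prespecified safety variable nor tied to an infusion window, so the planned organ-class comparison is insensitive to them wherever background events are common

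*Combined protocol and SAP*

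**What the plan says.** The section Safety variables lists "Postoperative mortality (30 days + in-hospital), stroke within 24 hours of surgery and SUSAR" and nothing else.

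The hazards are named in three other places. Overall assessment of risk and benefit states that "The risk of adverse reactions, such as Chinese restaurant syndrome, asthma or urticaria is considered small with the dosages employed", adds that none has been seen in twenty years of use, and concludes that benefit outweighs hazard. Adverse reactions and toxicology describes the syndrome as flushing, headache and chest pain, alongside asthma and urticaria. Discontinuation of the infusion treats bronchial obstruction, rash and anaphylaxis as signs for ending the infusion.

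Adverse events (AE) says how events are analysed. All are registered and split into serious and non-serious, and "To determine if the study substance had any influence on AE these events will be compared between treatment group and control group". The grouping is anatomical: "AE will be reported according to what organ has been affected: Central nervous system, heart - circulation, lungs, gastrointestinal tract, kidneys, skin". Infections, and nausea needing antiemetics, are reported in their own right. Hypersensitivity and infusion reactions are not, and no time window is given. On background the section says "Adverse events (AE) are common after cardiac surgery as all patients have some degree of postoperative pain, bleeding and fever", and that atrial fibrillation "is observed in approximately one third of the patients undergoing CABG".

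**The concern.** The reactions on which the benefit-risk statement rests have no place of their own in the analysis. SUSAR, in its usual sense, requires a reaction to be serious and unexpected. A non-serious rash or flush never qualifies, and a serious bronchospasm may not if it is regarded as already described.

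What remains is the organ table. It divides one syndrome between skin, central nervous system and heart, and puts bronchospasm among all postoperative lung events, whenever they occurred. No section compares infusions ended early between the arms.

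The trial could therefore report no SUSAR and no difference by organ although glutamate caused reactions in a few percent of patients. That result would be read as support for the statement that these reactions have not been observed.

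**Working it through.** **Inputs from the protocol.** 310 patients allocated 1:1, so 310/2 = 155 per arm. Two-sided 5% level. Chi-square test, or Fisher's exact test when an expected count is below 5 (Sample size estimation and statistics). Atrial fibrillation in about one third of CABG patients.

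**Assumed inputs.** The protocol gives no rate for the named reactions and no background rate for lungs or skin. I take a 5% reaction rate (2% as a lower case) and backgrounds from 0 to 20%, plus the documented one third.

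**The plan's own figure.** Δ = 7112 − 5261 = 1851. SD = √((4409² + 6454²)/2) = 5527. n = 2 × (1.960 + 0.842)² × 5527²/1851² ≈ 140 per arm. The t-based calculation first reaches 80% at 141 (power 0.8002), so the stated 141 is reproduced. It was set for NT-proBNP; no figure is given for detecting reactions.

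**Dedicated item, zero background.** Against 0 of 155, the Fisher p-value for k cases is 2 × C(155,k)/C(310,k). This gives 0.060 for k = 5 and 0.030 for k = 6, so six cases are needed. Power is P(X ≥ 6) with X ~ Binomial(155, rate): 79% at a 5% rate and 9% at 2%.

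**The same reactions inside an organ class.** Let b be the background in both arms. If reactions occur independently of other events, the glutamate rate is b + 0.05(1 − b). If they fall only on patients with no other event in the class, it is b + 0.05. Power is by exact enumeration of both binomials with the planned test:

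| Background b | Power, independent | Power, full 5-point excess |
|---|---|---|
| 0 (dedicated item) | 79.2% | 79.2% |
| 1% | 64.3% | 65.1% |
| 5% | 35.4% | 38.2% |
| 10% | 22.7% | 26.5% |
| 20% | 13.7% | 18.5% |
| one third | 9.5% | 15.2% |

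**Illustration.** Take 31 of 155 (20%) with a lung event in each arm, plus six extra on glutamate: 37 v 31. Expected counts are 34, so chi-square applies: (37 − 31)² × 310/(68 × 242) = 0.68, p = 0.41. The same six cases as a separate item, 6 v 0, give p = 0.030. Six is the smallest number that reaches significance against zero, so this example flatters the separate item. The table is the fairer summary.

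**If no case is seen.** Zero of 155 gives a one-sided 95% upper limit of 1 − 0.05^(1/155) = 1.9%. An organ-class total gives no such bound for a specific reaction.

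**The case against.** A reader might infer that the trial cannot detect these reactions at all. The documents do not support that. All adverse events are registered and compared between arms, and reporting by organ does not forbid listing individual terms. Bronchial obstruction, rash and anaphylaxis are looked for at the bedside as reasons to end the infusion. Codes may be broken for a suspected reaction. SAEs reach the sponsor within 24 hours, and suspected side effects, not only SUSARs, go to the agency and the ethics board. This stands for individual cases. It does not supply a prespecified randomised comparison, because it depends on someone suspecting a reaction.

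A reader might also infer that every organ class is crowded with surgical events. The only rate given is for atrial fibrillation, which belongs to heart and circulation. Pain, bleeding and fever are not assigned to a class. Skin, where rash, urticaria and flushing would be counted, may have a low background, and there the loss would be modest.

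Three further points stand in part:

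- **Rarity.** The 5% rate is assumed, while the protocol reports none of these reactions so far and excludes patients with suggestive food allergy. At 2% or less the limit is sample size, which a new item does not cure, although it would still yield an interpretable count and upper limit.
- **Unseen documents.** The text does not define which reactions are expected. The investigator's manual, the toxicology supplement and the CRF are not available and may say more.
- **Headache and chest pain.** An anaesthetised or ventilated patient cannot report them. That comes with the setting and is not a planning error. The ventilation times in Table 2 (medians 5.0 and 7.4 hours) come only from patients with LV failure, so they are indirect evidence on how long this lasts.

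**Conclusion.** The point holds as a gap in prespecification and as a cheap improvement. The named reactions are not a safety variable unless they qualify as SUSAR, no infusion window is defined, and neither these reactions nor early-ended infusions are compared between arms as such.

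On an assumed 5% reaction rate, folding the reactions into an organ class takes power from 79% to roughly a quarter at 10% background and to 14 to 18% at 20%. At 1% background it remains 64 to 65%. The direction is the same under both overlap assumptions, but the size depends on lung and skin backgrounds that the documents do not give. The one documented rate, one third, concerns a class that would mainly receive chest pain, the symptom hardest to assess here. The 79% is also a ceiling for any new item, since a composite will have some background of its own.

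Nothing here touches the primary endpoint or the monitoring of mortality and stroke. What is affected is how far a negative safety result can support the protocol's statement about its own named hazards.

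**What to change.** In Safety variables, make two additions:

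1. All suspected serious adverse reactions, whether expected or not, alongside SUSAR.
2. One prespecified composite: any of rash or urticaria, flushing, bronchial obstruction, anaphylactic reaction, or an infusion ended early under the existing discontinuation section. Record it from the start of infusion to a fixed time after its end. Report the number in each arm, the difference with a confidence interval, and the components separately.

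Keep the organ-class table as it is. State that no conclusion will be drawn on headache and chest pain while patients are anaesthetised or ventilated, and that the composite is not powered for reaction rates of about 2% or less.

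The cost is one extra line on the CRF, which is already completed when the infusion starts, and one row in the safety table. The sample size is unchanged, and no change to the rule for ending the infusion is proposed.
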